6.8.1 Primary Efficacy Analysis

CCI

The primary efficacy endpoint is the Sum of Pain Intensity Difference over 8 hours (SPID0-8).

For each post-dose time point, PIDs will be derived by subtracting the pain intensity at the post-dose time point from the baseline intensity score (baseline score – post-baseline score). A positive difference is indicative of improvement. The time-weighted sum of pain intensity differences over 8 hours (SPID0-8) will be calculated by multiplying the PID score at each post-dose time point by the duration (in hours) since the preceding time point and then summing these values over 8 hours.

CCI

6.8.2 Secondary Efficacy Analysis

6.8.2.1 Total Pain Relief over 8 hours

Total Pain Relief over 8 hours (TOTPAR0-8) will be calculated by multiplying the pain relief score at each post-dose time point by the duration (in hours) since the preceding time point and then summing these values over 8 hours. Nominal times as recorded by the site will be used for time points mentioned above.

TOTPAR0-8 will be analyzed in an analogous manner to the primary endpoint, SPID0-8.

6.8.2.2 Time to First Use of Rescue Medication

Time to first use of rescue medication during the treatment period will be analyzed.

Time to first use of rescue medication will also be presented in a by-subject listing.

6.8.2.3 Sum of Pain Intensity Differences, SPID0-2, SPID0-4, SPID0-12

SPID0-2, SPID0-4 and SPID0-12 will be calculated for 2, 4, and 12 hours by multiplying the PID score at each post-dose time point by the duration (in hours) since the preceding time point and then summing these values over 2, 4, and 12 hours, respectively.

The SPID 0-2, 0-4, and 0-12 will be analyzed similarly as to the primary endpoint.

6.8.2.4 Total Pain Relief, TOTPAR0-2, TOTPAR0-4, TOTPAR0-12, TOTPAR8-12

Total pain relief from 0 to 2, 4, and 12 hours, and 8-12 hours (TOTPAR0-2, TOTPAR0-4, TOTPAR0-12, TOTPAR8-12) will be calculated by multiplying the pain relief score at each post-dose time point by the duration (in hours) since the preceding time point and then summing these values. Nominal times as recorded by the site will be used for time points mentioned above.

TOTPAR0-2, TOTPAR0-4, TOTPAR0-12, and TOTPAR8-12 will be analyzed in an analogous manner to the primary endpoint, SPID0-8.

6.8.2.5 Pain Intensity Difference (PID) and Pain Relief

PIDs will be derived by subtracting the pain intensity at the post-dose time point from the baseline intensity score (baseline score – post-baseline score). A positive difference is indicative of improvement. Pain intensity scores and PIDs at 0.5, 1, 1.5, 2, 3, 4, 5, 6, 7, 8, 9, 10, 11, and 12 hours post-dose will be summarized using descriptive statistics for each treatment group. In addition, line graphs showing the time effect curves will be presented by treatment group.

6.8.2.6 Peak PID and Peak Pain Relief

Peak PID and peak pain relief will be summarized using descriptive statistics for each treatment group.

6.8.2.7 [Redacted]

[Redacted]

[Redacted]

[Redacted]

[Redacted]

[Redacted]

6.8.2.9 Cumulative Proportion of Subjects Taking a Rescue Medication

The cumulative proportion of subjects taking rescue medication by each time point will be summarized [Redacted]. In addition, the cumulative proportion of subjects taking rescue medication will be plotted at every time point for each treatment group to show the time-effect. The number of times a subject took a rescue medication over the 12-hour period will be summarized using frequency counts and percentages by treatment group.

6.8.2.10 [Redacted]

[Redacted]

CCI

6.8.2.11 Global Assessment Scores

The global assessment score will be summarized using frequency counts and percentages as well as with descriptive statistics.

6.9 Safety Evaluation

Only descriptive analyses will be presented for the Safety population. No imputation will be made for missing safety data. Quantitative data for safety variables will be described by summary statistics for the original data as well as for the differences to baseline when it is appropriate. Frequency tables will be provided for qualitative data.

6.9.1 Extent of Exposure

Study treatment administration data will be presented with a by-subject listing.

6.9.2 Adverse Events

All AEs that occur during the study will be recorded and classified on the basis of Medical Dictionary for Regulatory Activities (MedDRA) terminology. Treatment-emergent AEs (TEAEs) are defined as AEs with an onset on or after the date of the first study drug administration. AEs noted prior to the first study drug administration that worsen after baseline will also be reported as AEs and included in the summaries.

TEAEs will be summarized by treatment group, the number of subjects reporting a TEAE, system organ class, preferred name, severity, relationship to study treatment (causality), and seriousness. When summarizing TEAEs by severity and relationship, each subject will be counted once within a system organ class or a preferred term by using the event with the highest severity and greatest relationship within each classification.

Serious AEs (SAEs) will be summarized.

The number and percent of subjects who experience any event, by System Organ Class (SOC), and by Preferred Term (PT) will be displayed by treatment group for the Safety population.

All adverse events and all serious adverse events will be presented in individual listings. In addition, a list of subjects who prematurely discontinue from the study due to an AE will be provided.

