#### Treatment Phase

Following selection, qualified participants will enter the Treatment Phase and be scheduled for their surgical teeth extractions. After completion of the surgical teeth extractions, participants will remain at the study site for observation. Participants with appropriate pain requirement will be randomized into one of seven (7) treatment groups. Participants will rate their pain severity and pain relief over the next 12 hours. Onset of analgesia will be measured using a two stopwatch approach. The first stopwatch will be used to capture the time when any pain relief is first perceived and in certain cases, the second stopwatch will be used to capture the time when pain relief becomes meaningful to the participant. After completion of all trial procedures, participants will be discharged from the study site.

All participants are required to remain at the study center and complete all assessments regardless of rescue.

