### **6.5.1 Rescue Medicine**

If adequate pain relief was not achieved, then participants are permitted to take rescue medication, although they will be encouraged to wait 2 hours to allow the investigational product time to take effect. The study site will supply the rescue medication that will be obtained locally. Rescue medication will be Hydrocodone 5 mg/Acetaminophen 325 mg tablets or other appropriate analgesics may be used at the discretion of the Investigator. Rescue medication is also available on return of pain and the time of rescue medication will be recorded. Pain assessments will be performed immediately before the first dose of rescue medication.

- Rating of Pain Intensity (NRS);
- Rating of Pain Relief (Categorical);
- Global Assessment of investigational product as a pain reliever.

All active stopwatch elapsed time(s) will be stopped at the time of rescue administration and recorded on the case report form.

Participants will be queried in a nonspecific fashion for any adverse events. All observed and reported AEs will be collected and recorded on the case report form. The information recorded will be based on signs and symptoms reported by the participant or observed by the research coordinator during clinical evaluation.

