## **8.2 Safety Assessments**

Safety measures will be analyzed for all participants in the safety population.

Adverse events will be collected throughout the treatment and safety follow-up periods and will be coded using the Medical Dictionary for Regulatory Activities (MedDRA) dictionary. Only treatment-emergent AEs will be included, i.e., AEs that begin or worsen after the first dose of the investigational products in the treatment period. The number and percent of participants who experience any event, by System Organ Class (SOC), and by Preferred Term will be displayed by treatment group. Tables will also be produced by severity and relationship to investigational product. Seriousness, severity, relationship to investigational product, duration, and outcome will also be listed.

Planned time points for all safety assessments are provided in the SoA.

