### **8.3.1 Time Period and Frequency for Collecting AE and SAE Information**

All AEs and SAEs will be collected from the signing of the ICF until the follow up visit at the time points specified in the SoA (Section 1.3).

Medical occurrences that begin before the start of study intervention but after obtaining informed consent will be recorded on the Medical History/Current Medical Conditions section of the case report form (CRF) not the AE section.

All SAEs will be recorded and reported to the sponsor or designee immediately and under no circumstances should this exceed 24 hours, as indicated in Section 10.3.2. The investigator will submit any updated SAE data to the sponsor within 24 hours of it being available.

Investigators are not obligated to actively seek AE or SAE after conclusion of the study participation. However, if the investigator learns of any SAE, including a death, at any time after a participant has been discharged from the study, and he/she considers the event to be reasonably related to the study intervention or study participation, the investigator must promptly notify the sponsor.

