3. STUDY OBJECTIVES

The primary objective of this study will be to compare a single oral dose of the FDC relative to naproxen sodium CCI Caffeine CCI and placebo.

The secondary objectives of this study will be to:

- To compare a single oral dose of the FDC relative to naproxen sodium CCI Caffeine CCI and placebo. The assessments are made in terms of:
 - Pain intensity differences Measures of pain relief
 - Duration of analgesic efficacy
 - CCI
 - CCI
 - Overall relief from pain based on measures of pain intensity and pain relief
 - Global assessment of the investigational product
- CCI
- To assess the safety and tolerability of the investigational product in terms of adverse events (AEs) and clinical parameters

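### TEAEs are tabulated by treatment group without relating onset to first rescue, so rescue-drug events can enter the descriptive tolerability comparison

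*SAP*

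**What the plan says.** **What is tabulated.** SAP 6.9.2: "TEAEs will be summarized by treatment group, the number of subjects reporting a TEAE, system organ class, preferred name, severity", then relationship and seriousness. The window opens at dosing: "Treatment-emergent AEs (TEAEs) are defined as AEs with an onset on or after the date of the first study drug administration". Protocol 8.3.1 sets the collection period: "All AEs and SAEs will be collected from the signing of the ICF until the follow up visit", and the Schedule of Activities places that contact 2 to 5 days after discharge.

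**What rescue is.** Protocol 6.5.1: "Rescue medication will be Hydrocodone 5 mg/Acetaminophen 325 mg tablets or other appropriate analgesics may be used at the discretion of the Investigator". It is permitted when relief is inadequate or pain returns. Participants are encouraged, not required, to wait 2 hours, and the time of rescue is recorded. Repeat rescue is foreseen, because Protocol 9.4.1 tabulates how often each participant took it.

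**What happens after rescue.** Protocol 4.1, Treatment Phase: "All participants are required to remain at the study center and complete all assessments regardless of rescue". For efficacy, Protocol 9.4.1 replaces pain scores after rescue with imputed values. No legible text gives a counterpart for adverse events. SAP 6.7 and 6.8.2.9 summarise rescue use separately and do not link it to event onset.

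**What the comparison is for.** SAP 3 lists as a secondary objective "To assess the safety and tolerability of the investigational product in terms of adverse events (AEs) and clinical parameters", and Protocol 4.2 names the side-effect profile of the FDC against its components as something the design is meant to measure. SAP 6.9 makes all safety analyses descriptive.

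**The concern.** Rescue brings in a second active drug, and the trigger for it is failure of the study drug. If rescue use differs between arms, the all-TEAE table shows study drug plus rescue drug in proportions that vary by arm. Events caused by the rescue analgesic would then raise the rate most where rescue is most common, which one would expect to be placebo and caffeine alone. A true excess of events on an FDC arm could look smaller than it is, or disappear.

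The efficacy analysis protects itself against this and the safety analysis does not. Participants who rescue within 60 minutes show the contrast best. Protocol 9.3 removes them from the PP population, but they stay in the Safety population, where nearly all their observation time follows rescue.

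At stake is how the tolerability of the FDC is read from the tables, not any hypothesis test.

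**Working it through.** **Plan's own figures.** The point rests on no stated number. The arm sizes used below come from Protocol 9.2: five arms of 30 and two of 15 give 5 × 30 + 2 × 15 = 180, and 180 / 0.95 = 189.5, rounded up to 190. Both match the plan.

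**Inputs not in the documents (assumptions).**
- a, the AE risk without rescue: 10% to 20%.
- h, the added AE risk in a rescued participant: 10% to 30%.
- r, the share rescued, placebo against one active arm: from 50% v 50% to 80% v 30%.

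**Model.** With the two sources independent, P(any TEAE) = 1 − (1 − a)(1 − r·h). If a is the same in both arms, the true difference is 0 and the tabulated placebo excess is (1 − a) × h × (r_placebo − r_active).

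| a | h | rescue, placebo v active | placebo | active | placebo excess |
|---|---|---|---|---|---|
| 10% | 30% | 80% v 30% | 1 − 0.9 × 0.76 = 31.6% | 1 − 0.9 × 0.91 = 18.1% | 13.5 points |
| 10% | 20% | 80% v 30% | 1 − 0.9 × 0.84 = 24.4% | 1 − 0.9 × 0.94 = 15.4% | 9.0 points |
| 20% | 10% | 60% v 50% | 1 − 0.8 × 0.94 = 24.8% | 1 − 0.8 × 0.95 = 24.0% | 0.8 points |
| any | any | 50% v 50% | equal | equal | 0 |

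The largest value is 0.135 × 15, about 2 of 15 placebo participants.

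**Masking a real excess.** Let the active arm have a = 20% and placebo a = 10%, a true excess of 10 points.
- h = 10%, rescue 60% v 50%: 24.0% − 15.4% = +8.6 points.
- h = 20%, rescue 80% v 30%: 24.8% − 24.4% = +0.4 points.
- h = 30%, rescue 80% v 30%: 27.2% − 31.6% = −4.4 points.

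**Against sampling error, 30 v 15 participants.** SE = √[p(1 − p)(1/30 + 1/15)]. This is √(0.09 × 0.1) = 9.5 points at p = 10% and √(0.16 × 0.1) = 12.6 points at p = 20%. In the most extreme row, using its own rates, √(0.316 × 0.684/15 + 0.181 × 0.819/30) = 13.9 points. The distortion therefore runs from nothing to about one standard error.

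**The case against.** **The planned table is legitimate.** All TEAEs by arm is a proper treatment-policy summary of what followed assignment. The trial is not powered (Protocol 9.2) and safety is descriptive, so no inference is invalidated. This stands: what is missing is a supplement.

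**Causality already deals with rescue.** Protocol 10.3.3 has the investigator weigh other explanations, concomitant therapy among them, and the timing of the event relative to the study dose. Investigators are blinded, and SAP 6.9.2 summarises by relationship. This is a real safeguard, but a partial one. It is a yes/no judgement about study drug with no category for rescue, and the all-causality SOC and preferred-term table does not use it.

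**The split has its own bias.** Ending observation at rescue shortens time at risk most in the arms that rescue early, and for a reason tied to outcome. Participant-hours only partly correct for this. This also stands, so the split tables can only be supportive.

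**Feasibility.** The documents do not say that AE onset clock times are captured. That limits precision but does not prevent the split. Rescue time is recorded, AEs are queried at each pain assessment (Protocol 8.1.6), and Protocol 6.5.1 also calls for an AE query.

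**Stronger readings that the documents do not support.**
- A reader might infer that the comparison is biased towards the FDC as a matter of fact. No rescue rates by arm are given, rescue may be an analgesic other than the opioid combination, and with equal rescue the effect is zero.
- A reader might extend the point to FDC against naproxen alone. Protocol 4.3 anticipates that one caffeine dose will not potentiate naproxen. For that dose nothing suggests different rescue use, and for the others no size can be given.
- A reader might want hour-12 vital signs split by rescue. That compares small self-selected subsets: at 60% to 80% placebo rescue, 3 to 6 of 15 would be unrescued. Protocol 8.1.6 already provides a 1-hour reading that is largely before rescue.

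**Conclusion.** The gap holds in the legible text: SAP 6.9.2 neither ends the TEAE window at first rescue nor classifies onset relative to it. SAP 6.1, 6.4 and part of section 8 are blacked out, but 6.9.2 shows no redaction. Because the Safety population text is among the redactions, the table can only be described as by treatment group; whether that means randomised or actual treatment cannot be checked.

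The consequence is one of interpretation. Read alone, the planned table can mix rescue-drug events into the tolerability comparison, chiefly FDC against placebo or caffeine alone. The range of 0 to 13.5 points rests entirely on assumed rescue rates, assumed rescue-related AE risk and independence of the two sources. The direction rests on the inference that less effective arms rescue more. This is a worthwhile, inexpensive improvement, not an error that invalidates the safety analysis.

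**What to change.** In SAP 6.9.2:

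1. Keep the planned TEAE tables unchanged.
2. Add two descriptive SOC and preferred-term tables by arm: onset after dosing and before first rescue, and onset after first rescue. Show participant-hours at risk beside the counts, and state where the pre-rescue window ends for participants who never rescue.
3. Classify by AE onset time where recorded. Otherwise, classify by whether the event was reported at or before the query made at rescue.
4. State that the FDC tolerability conclusion will be read from the overall and pre-rescue tables together. Label the split tables supportive, because pre-rescue observation is shorter and informatively truncated in arms that rescue early.

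The cost is one derived flag and two extra tables, using the recorded rescue time and the AE queries already planned. It changes nothing in treatment, rescue or the assessment schedule.

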6.9.3 Clinical Laboratory Evaluation

Urine pregnancy tests will be presented in a by-subject listing.

Urine drug screens taken during screening and pre-surgery will be presented in a by-subject listing.

6.9.4 Other Observations Related to Safety

6.9.4.1 Vital Signs

Vital signs data for blood pressure, pulse rate, and respiratory rate will be summarized using descriptive statistics by treatment group for both the observed values and change from baseline values.

Blood pressure measurements are collected in triplicate at each timepoint. Prior to computing summary statistics, the mean of each measurement will be calculated for each subject at each timepoint. Summary statistics will be computed from each subject's mean blood pressure values at each timepoint. Individual vital sign data, as well as means of blood pressure triplicates, will be presented in a by-subject listing.

6.9.4.2 Physical Examination

[figure not shown]
Physical examination data will be presented in a by-subject listing.

6.9.4.3 Electrocardiogram (ECG) Measurements

Not applicable to this study.

[figure not shown]
7. DETERMINATION OF SAMPLE SIZE

CCI

8. CHANGES IN THE PLANNED ANALYSES

CCI

Also, TOTPAR8-12 is included and analyzed similarly to other TOTPARs.
